#### **8.6 DEFINITION OF VISIT WINDOWS**

Table 4 of the protocol presents the schedule of procedures/Assessments. Some procedures/assessments are performed at 3 months, 6 months or yearly intervals. Table 8 presents the protocol specified visits/months and corresponding time windows used for visit-wise analyses are presented in terms of days relative to the first dose. For subjects that are randomized, the last available assessment on or before the randomization date will be used as the Baseline-Day 1. If more than one measurement is included in a visit window, the measurement collected closest to the scheduled date will be used in the analysis. In the case where two measurements were collected an equal number of days before and after the Scheduled Day the later of the two measurements will be used for analysis.

For ECHO and PAH assessments when assessing a new or worsened event then the most severe assessment will be selected if 2 or more assessments fall within a visit window.

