- b. Assessments are only to be performed if clinically indicated or necessary due to state controlled substance requirements. (revised per Amendment 01)
- c. Window ±10 days for all visits after Visit 2, other than the EOS visit which has a window of +10 days. Month is shown unless otherwise indicated; 1 month = approximately 30 days.
- d. Only for a subset of subjects at selected sites. Baseline echocardiograms will be performed in between Visits 1 and 2, after the results of screening assessments have been obtained but prior to randomization, and subject eligibility is confirmed. ECHOs will be performed until at least 1000 subjects have completed the Month 36 echocardiographic assessment. (revised per Amendment 02)

Table 4 Schedule of Procedures/Assessments in Study APD356-G000-401

Phase	Pre-randomization	Randomization																		
Period	Screening	Treatment																	F/U	
Visit	1	2 ^a	3	4	5	6	7	8	9	10	11	12	13	14	15	16	17	EOT	EOS	Unsch ^b
Month ^c	Days -30 to -1	Day 1	3	6	9	12	15	18	21	24	28	32	36	40	44	48	52	56		
Assessment (revised per Amendment 01)																				

- e. For subjects who discontinue study drug early, these assessments will be stopped after the EOT visit.
- f. Renal function parameters and glycemic profile should be obtained at all specified visits, regardless of study drug status. (revised per Amendment 01)
- g. Serum cystatin C will be measured at Baseline and yearly thereafter in the subpopulation with CKD Stage 1 or 2 at Baseline. Serum creatinine will be measured in chemistry blood samples if chemistry assessments are performed.
- h. Serum pregnancy tests will be conducted at Screening. A urine pregnancy test will be conducted at randomization.
- i. These assessments should be done if a telephone contact is performed in lieu of a clinic visit.

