- The change from baseline in eGFR and ACR will be analyzed using a mixed-effects model with repeated measures with treatment, month and month by treatment interaction as a factor and baseline value as a covariate. Comparison of the trajectories for lorcaserin HCl and placebo will be made at 1 year, yearly thereafter, and at EOS. The estimated treatment difference in the LSM between lorcaserin HCl and placebo, p-value, and the two-sided 95% CI will be calculated. The ITT will be used for this analysis. SAS PROC MIXED will be used using an unstructured covariance matrix (TYPE=UN). If the model fails to converge then a Heterogeneous Toeplitz covariance structure (TYPE=TOEPH) will be used.
- The change from Baseline in echocardiographically-determined pulmonary arterial systolic pressure will be analyzed using a mixed-effects model with repeated measures with treatment, month, month by treatment interaction as factors and baseline pulmonary arterial systolic pressure and baseline BMI as covariates. Comparison between lorcaserin HCl and placebo will be made at 2 years and yearly thereafter. The estimated treatment difference in the LSM between lorcaserin HCl and placebo, p-value, and the two-sided 95% CI will be calculated. The ITT will be used for this analysis. SAS PROC MIXED will be used using an unstructured covariance matrix (TYPE=UN). If the model fails to converge then a Heterogeneous Toeplitz covariance structure (TYPE= TOEPH) will be used.
- Change from Baseline in HbA1c, FPG, fasting insulin levels, and homeostatic model assessment insulin resistance (HOMA-IR), at 6 months in subjects with T2DM at Baseline will be analyzed using an ANCOVA model with treatment and stratification variable (presence of established CV disease or CV risk factors without established CV

disease) as factors, and baseline HbA1c, as a covariate. Comparison between lorcaserin HCl and placebo will be made at 6 months. The estimated treatment difference in the LSM between lorcaserin HCl and placebo, p-value, and the two-sided 95% CI will be calculated. The T2DM Analysis Set will be used for this analysis, in the following subpopulations.

- o Subjects with (HbA1c>7%) at Baseline
- o Subjects who have not been treated with antidiabetic agents at Baseline
- o Subjects who are on monotherapy with oral antidiabetic agent at Baseline
- Subjects with early T2DM (duration of diagnosis of diabetes is less than 5 years) at Baseline.

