#### 6 INTERIM ANALYSES

There will be one interim analysis; when 460 adjudicated MACE events have occurred, the primary analysis for MACE will be conducted. This will be the analysis to rule out a hazard ratio of 1.4. If the non-inferiority margin is met, the study will continue to accrue events until the required number of MACE+ and diabetes conversion events have occurred.

The interim analysis for MACE endpoint will be performed by an independent statistician and governed by an independent DMC and is anticipated to occur on or before (approximately) July 2017. The interim analysis will be conducted according to a DMC Charter to establish whether the MACE primary objective has been achieved.

To maintain the integrity and credibility of the trial, procedures will be implemented to ensure the DMC and independent statistician have sole access to evolving information from the clinical trial regarding comparative efficacy and safety data aggregated by treatment group. Full details of the DMC procedures including primary responsibilities of the DMC, its relationship with other trial components, its membership, and the purpose and timing of its meetings will be documented in the DMC Charter. These details will also include procedures to ensure confidentiality and proper communication, the safety and statistical monitoring guidelines to be implemented by the DMC, and an outline of the content of the closed reports and open reports that will be provided to the DMC. See Appendix 13.1.2 for the DMC charter. In addition, the Study Integrity Charter in Appendix 13.1.2, describes the membership, responsibilities, data access, and firewalls, when 460 adjudicated MACE events are achieved and the IA is conducted.

At the interim analysis for MACE, the estimate of the hazard ratio of lorcaserin HCl to placebo and the corresponding one-sided 97.5% CI will be calculated. Non-inferiority between lorcaserin HCl and placebo will be declared if the upper limit of the 97.5% CI is less than the non-inferiority margin of 1.4. Otherwise, lorcaserin HCl will be declared as not noninferior to placebo and the trial will stop.

If non-inferiority between lorcaserin HCl and placebo is confirmed when 460 adjudicated MACE events are observed at approximately 43 months from the start of the study, then the study will be continued to observe 1401 adjudicated MACE+ events at approximately 54 months from the start of the study, and 2.5 years median treatment duration.

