**Table 8 Visit Windows Measurements** 

Scheduled Visit	Scheduled Month	Scheduled Day	Time Window (Days)		(Days Mo Inte	Vindow ) For 6 onth erval sments	Time W (Days Yea Inte Assess	) For arly rval
1	Screening		-30	-1				
2	Baseline/ Randomization	1	1		1		1	
3	3	90	2	135				
4	6	180	136	225	2	270		
5	9	270	226	315				
6	12	360	316	405	271	450	2	540
7	15	450	406	495				
8	18	540	496	585	451	630		
9	21	630	586	675				
10	24	720	676	780	631	810	541	900
11	28	840	781	900				
12	32	960	901	1020				
13	36	1080	1021	1140			901	1260
14	40	1200	1141	1260				
15	44	1320	1261	1380				
16	48	1440	1381	1500			1261	1620
17	52	1560	1501	1620				
EOT	56	1680	1621	1710				
EOS	58	1740	1711	Open				

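### SAP Table 8 fixes EOT and EOS by study day although the trial ends on one common date, so if the table is followed few or no subjects have an EOS value for the exploratory eGFR and ACR comparison

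*SAP*

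**What the plan says.** SAP 8.6 states that the "corresponding time windows used for visit-wise analyses are presented in terms of days relative to the first dose". When a window holds several measurements, the one nearest the scheduled day is used. The last rows of Table 8 read "EOT 56 1680 1621 1710" and "EOS 58 1740 1711 Open": visit, month, scheduled day, first and last day of the window. The last row with a yearly-interval window is "16 48 1440 1381 1500 1261 1620", so that column ends at day 1620 and has no EOT or EOS window.

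SAP 5.8 plans an eGFR and ACR comparison that "will be made at 1 year, yearly thereafter, and at EOS".

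Other sections treat these visits differently:

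- SAP 3.3: subjects stay in until a common study completion, not for a set number of visits. SAP 3.3.2.2 puts EOS 30 (+10) days after the last dose for those who complete treatment.
- SAP 8.5: the individual EOS date is that subject's last visit or contact.
- SAP 5.6.3: EOT for laboratory values is the last on-treatment value.
- Protocol 9.5.5.1: a subject who stops drug early has the EOT visit within about 30 days, whatever the study day.

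**The concern.** Calendar-driven visits are being sorted by a rule meant for scheduled months. With a common stop and staggered entry, the EOS study day depends mainly on the randomization date. Applied literally, Table 8 keeps the EOS label for those randomized first and files everyone else's final sample under an ordinary month. An early discontinuer's EOT sample is relabelled in the same way.

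Two things are at stake. The EOS contrast for eGFR and ACR could rest on an unrepresentative early slice or on nobody. The Month 48 contrast, which is also planned, could take in samples drawn about 30 days after the last dose without this being stated. Two programmers reading 8.6 and 8.5 could build different EOS populations.

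**Working it through.** **Inputs.** Month convention: "1 month = approximately 30 days" (Protocol Table 4, footnote c). Final target: "1401 adjudicated MACE+ events at approximately 54 months from the start of the study" (SAP 6). SAP 4: N = 12,000, 15-month accrual, MACE+ background rate 3.5% per year, dropout 5% per year, 15% risk reduction, 2-sided α = 0.05. EOS 30 to 40 days after last dose (SAP 3.3.2.2). Assumed here: uniform accrual and 30.4375 days per calendar month.

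**1. Table 8's own figure.** 56 × 30 = 1680 and 58 × 30 = 1740. The midpoint is (1680 + 1740)/2 = 1710, so EOS opens on day 1711. Reproduced.

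**2. The 54-month timeline.** Schoenfeld power for 1401 events at HR 0.85 is 0.860, against the stated >85%. Expected events are N × λ/(λ+η) × (1 − exp(−(λ+η)f)), averaged over follow-up f of 39 to 54 months. The result is 1385 to 1405, depending on how annual rates are converted to hazards, with the background rate in both arms. This reproduces 1401. With HR 0.85 in one arm it is 1287 to 1305, so completion could come later than 54 months.

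**3. EOS day at 54 months, prompt close-out.**

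- First subject: 54 × 30.4375 = 1644; plus 30 to 40 gives day 1674 to 1684.
- Accrual span: 15 × 30.4375 = 456.6 days, so the last subject's EOS is on day 1217 to 1227.
- Share reaching day 1711: 0%.
- Where the EOS samples land (30-day follow-up): 9.6% in the yearly Month 36 window, 78.9% in Month 48, and 11.5% on days 1621 to 1710, which is the general EOT window and lies outside every yearly window.

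**4. Other timelines.** Share = (longest study day − 1711)/456.6.

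| Timeline | Longest EOS day | Share in EOS window |
|---|---|---|
| 54 months, EOT visits 60 to 90 days after notification (assumed lag) | 1734 to 1774 | 5% to 14% |
| 56-month Randomization Phase, follow-up included (SAP 3.3.2) | 1704.5 | 0% |
| Notification at 56 months, EOS 30 to 40 days later | 1734 to 1744 | 5% to 7% |
| Last visit 31 October 2018, first randomization assumed 1 December 2013 to 30 January 2014 | 1735 to 1795 | 5% to 18% |
| Notification 1 to 31 October 2018, same start range, EOS 40 days later | 1745 to 1835 | 7% to 27% |
| 60 months from first screening to last visit (Protocol Synopsis), with or without 30 days of screening removed | 1796 to 1826 | 19% to 25% |

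**5. Displacement at Month 48 (yearly window 1261 to 1620, scheduled day 1440).** Take a completer whose EOT sample is about 30 days before EOS. With EOS on days 1291 to 1440, both samples are in the window and EOS is nearer day 1440. With EOS on days 1261 to 1290, the EOT sample falls in Month 36 and EOS stands in the Month 48 window without it. Either way the EOS sample becomes the Month 48 value.

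- 54 months: (1440 − 1261)/457 = 39% of completers.
- Notification at 58 months, earliest EOS day 1339: (1440 − 1339)/457 = 22%.

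**The case against.** The strongest reply is that nothing in the SAP says Table 8's EOS row governs the eGFR and ACR contrast. SAP 5.8 lists EOS apart from the yearly months, SAP 5.1.4 words the endpoint as the end of the study, and 8.5 and 5.6.3 already hold sensible definitions. Derivation rules sit in separate programming documents (SAP 9) that are not available here. This stands in part. The 8.5 definition appears under Censoring, however, whereas 8.6 is the section that claims visit-wise analyses. The conflict is therefore real even if programming later resolved it.

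Several stronger readings are tempting and not supported:

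- **No subject reaches day 1711, so the contrast is empty.** This holds only at 54 months with prompt close-out or at 56 months to last visit. The 54-month figure is a projected time to 1401 events, and completion also requires a 2.5-year median treatment duration.
- **About a third reach it at 60 months.** That adds 30 to 40 days of follow-up to a period that the Protocol Synopsis already runs to the last visit. The Synopsis also puts each subject on study for about 60 months. Read literally, everyone would pass day 1711, but a common stop at about 60 months after 15-month accrual rules that out.
- **The yearly column governs ACR.** It is the natural fit for a mostly yearly schedule, but no text maps parameters to columns.
- **On-treatment months are contaminated.** The analysis uses the ITT set, and renal parameters are collected regardless of drug status (Protocol Table 4, footnote f), so off-drug values are present by design. An attended Month 36 or Month 48 sample would normally win under the nearest-day rule. What remains is step 5: completers whose final visit comes at or before day 1440.

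**Conclusion.** The point holds as a wrong rule in SAP 8.6, not as proof that the EOS comparison cannot be estimated. The fixed-day EOT and EOS rows do not suit a common event-driven stop, and they contradict 8.5 and 5.6.3. Followed as written, they leave between none and roughly a quarter of subjects with an EOS value, all among the earliest enrolled, and relabel most actual EOS samples as scheduled months. At Month 48 they put a post-drug sample in place of the EOT sample for about 22% to 39% of completers on the two timelines worked.

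These sizes rest on uniform 15-month accrual, prompt visits unless a lag is stated, and the start-date range assumed for October 2018. A reader might infer a threat to the main results. There is none: the MACE, MACE+, T2DM-conversion and renal time-to-event analyses use event and censoring dates, not these windows. Only exploratory and descriptive visit-wise analyses are touched.

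**What to change.** In SAP 8.6:

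- Assign EOS by the nominal CRF visit, meaning the subject's final visit, consistent with 8.5.
- Assign EOT as the last on-treatment value, as in 5.6.3.
- Delete the EOT and EOS day rows from Table 8.
- Limit day windows to the scheduled months and keep EOS-visit samples out of them.

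Two related statements need reconciling at the same time: the sentence in SAP 8 that equates EOT with EOS for study completers, and the study-length figures of 54, 56, about 58 (December 2013 to October 2018) and 60 months.

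The cost is wording and the matching derivation code. No new data, visits or sample size are needed.

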**Table 8 Visit Windows Measurements** 

Scheduled Visit	Scheduled Month	Scheduled Day	Time Window (Days)		(Days Mo Inte	Vindow ) For 6 onth erval sments	Time W (Days Yea Inte Assess	) For arly rval
1	Screening		-30	-1				
2	Baseline/ Randomization	1	1		1		1	
3	3	90	2	135				
4	6	180	136	225	2	270		
5	9	270	226	315				
6	12	360	316	405	271	450	2	540
7	15	450	406	495				
8	18	540	496	585	451	630		
9	21	630	586	675				
10	24	720	676	780	631	810	541	900
11	28	840	781	900				
12	32	960	901	1020				
13	36	1080	1021	1140			901	1260
14	40	1200	1141	1260				
15	44	1320	1261	1380				
16	48	1440	1381	1500			1261	1620
17	52	1560	1501	1620				
EOT	56	1680	1621	1710				
EOS	58	1740	1711	Open				

#### 8.7 PROTOCOL DEVIATIONS

Protocol Deviations will be collected in the eCRF and included in the database. These protocol deviations will be review and monitored during the course of the study by the study team. Protocol deviations will rated as "Major" or "Minor" and finalized prior to data base lock.

#### 9 PROGRAMMING SPECIFICATIONS

The rules for programming derivations and dataset specifications are provided in separate documents.

#### 10 STATISTICAL SOFTWARE

All statistical analyses will be performed by Eisai Inc. or designee, using SAS Version 9.2 or later.

## 11 MOCK TABLES, LISTINGS AND GRAPHS (TLGS)

The study TLG shells will be provided in a separate document, which will show the content and format of all tables, listings, and graphs in detail.

## 13 APPENDICES

## 13.1 Sponsor's Grading for Determining Markedly Abnormal Laboratory Results

The following table of Sponsor's Grading for Laboratory Values is copied from the protocol, Appendix 5.**Sponsor's Grading for Laboratory Values** 

for Laboratory Values				
	Grade 1	Grade 2	Grade 3	Grade 4
BLOOD/BONE MARROW				
Hemoglobin	< LLN - 10.0 g/dL < LLN - 100 g/L < LLN - 6.2 mmol/L	< 10.0 - 8.0 g/dL < 100 - 80 g/L < 6.2 - 4.9 mmol/L	< 100 - 80  g/L	
Leukocytes (total WBC)	< LLN - 3.0 x 10  /L < LLN - 3000/mm 	< 3.0 - 2.0 x 10  /L < 3000 - 2000/mm 	< 2.0 - 1.0 x 10  /L < 2000 - 1000/mm 	< 1.0 x 10  /L < 1000/mm 
Lymphocytes	$< LLN - 800/mm^3$ $< LLN - 0.8 \times 10^9/L$	< 800 – 500/mm  < 0.8 – 0.5 x 10  /L	< 500 - 200/mm  < 0.5 - 0.2 x 10  /L	< 200/mm  < 0.2 x 10  /L
Neutrophils	< LLN - 1.5 x 10  /L < LLN - 1500/mm 	< 1.5 – 1.0 x 10  /L < 1500 – 1000/mm 	< 1.0 - 0.5 x 10  /L < 1000 - 500/mm 	< 0.5 x 10  /L < 500/mm 
Platelets	< LLN - 75.0 x 10  /L < LLN - 75,000/mm 	< 75.0 – 50.0 x 10  /L < 75,000 – 50,000/mm 	< 50.0 - 25.0 x 10  /L < 50,000 - 25,000/mm 	< 25.0 x 10  /L < 25,000/mm 
METABOLIC/ LABORATORY				
Albumin, serum- low (hypoalbuminemia)	< LLN - 3 g/dL < LLN - 30 g/L	< 3 – 2 g/dL < 30 – 20 g/L	< 2 g/dL < 20 g/L	life-threatening consequences; urgent intervention indicated
Alkaline phosphatase	> ULN – 3.0 x ULN	> 3.0 – 5.0 x ULN	> 5.0 – 20.0 x ULN	> 20.0 x ULN
ALT	> ULN $-3.0$ x ULN	> 3.0 - 5.0  x ULN	> 5.0 - 20.0  x ULN	> 20.0 x ULN
AST	> ULN $-3.0$ x ULN	> 3.0 - 5.0  x ULN	> 5.0 - 20.0  x ULN	> 20.0 x ULN
Bicarbonate, serum-low	< LLN $-$ 16 mmol/L	< 16 – 11 mmol/L	<11 – 8 mmol/L	< 8 mmol/L
Bilirubin (hyperbilirubinemia)	> ULN – 1.5 x ULN	> 1.5 - 3.0  x ULN	> 3.0 - 10.0  x ULN	> 10.0 x ULN
Calcium, serum-low (hypocalcemia)	< LLN - 8.0 mg/dL < LLN - 2.0 mmol/L	< 8.0 – 7.0 mg/dL < 2.0 – 1.75 mmol/L	< 7.0 – 6.0 mg/dL < 1.75 – 1.5 mmol/L	< 6.0 mg/dL < 1.5 mmol/L
Calcium, serum-high (hypercalcemia)	> ULN - 11.5 mg/dL > ULN - 2.9 mmol/L	> 11.5 – 12.5 mg/dL > 2.9 – 3.1 mmol/L	> 12.5 – 13.5 mg/dL > 3.1 – 3.4 mmol/L	> 13.5 mg/dL > 3.4 mmol/L
Cholesterol, serum-high (hypercholesterolemia)	> ULN - 300 mg/dL > ULN - 7.75 mmol/L	> 300 – 400 mg/dL > 7.75 – 10.34 mmol/L	> 400 - 500 mg/dL > 10.34 - 12.92 mmol/L	> 500 mg/dL > 12.92 mmol/L
Creatinine	> ULN – 1.5 x ULN	> 1.5 - 3.0  x ULN	> 3.0 - 6.0  x ULN	> 6.0 x ULN
GGT (γ-Glutamyl transpeptidase)	> ULN – 3.0 x ULN	> 3.0 - 5.0  x ULN	> 5.0 - 20.0  x ULN	> 20.0 x ULN
Glucose, serum-high (hyperglycemia)	Fasting glucose value: > ULN – 160 mg/dL > ULN – 8.9 mmol/L	Fasting glucose value: > 160 – 250 mg/dL > 8.9 – 13.9 mmol/L	> 250 – 500 mg/dL; > 13.9 – 27.8 mmol/L; hospitalization indicated	> 500 mg/dL; > 27.8 mmol/L; life-threatening consequences
Glucose, serum-low (hypoglycemia)	< LLN – 55 mg/dL < LLN – 3.0 mmol/L	< 55 – 40 mg/dL < 3.0 – 2.2 mmol/L	< 40 – 30 mg/dL < 2.2 – 1.7 mmol/L	< 30 mg/dL < 1.7 mmol/L life-threatening consequences; seizures
Phosphate, serum-low (hypophosphatemia)	< LLN - 2.5  mg/dL	< 2.5 – 2.0 mg/dL < 0.8 – 0.6 mmol/L	< 2.0 – 1.0 mg/dL < 0.6 – 0.3 mmol/L	< 1.0 mg/dL < 0.3 mmol/L

The following table of Sponsor's Grading for Laboratory Values is copied from the protocol, Appendix 5.**Sponsor's Grading for Laboratory Values** 

	Grade 1	Grade 2	Grade 3	Grade 4
				life-threatening consequences
Potassium, serum-high (hyperkalemia)	> ULN – 5.5 mmol/L	> 5.5 – 6.0 mmol/L	> 6.0 – 7.0 mmol/L hospitalization indicated	> 7.0 mmol/L life-threatening consequences
Potassium, serum-low (hypokalemia)	< LLN – 3.0 mmol/L	< LLN - 3.0 mmol/L; symptomatic; intervention indicated	< 3.0 – 2.5 mmol/L hospitalization indicated	< 2.5 mmol/L life-threatening consequences
Sodium, serum-high (hypernatremia)	> ULN - 150 mmol/L	> 150 – 155 mmol/L	> 155 – 160 mmol/L hospitalization indicated	> 160 mmol/L life-threatening consequences
Sodium, serum-low (hyponatremia)	< LLN – 130 mmol/L	N/A	< 130 – 120 mmol/L	< 120 mmol/L life-threatening consequences
Triglyceride, serum-high (hypertriglyceridemia)	150 – 300 mg/dL 1.71 – 3.42 mmol/L	> 300 – 500 mg/dL > 3.42 – 5.7 mmol/L	> 500 – 1000 mg/dL >5.7 – 11.4 mmol/L	> 1000 mg/dL > 11.4 mmol/L life-threatening consequences
Uric acid, serum-high (hyperuricemia)	> ULN − 10 mg/dL ≤ 0.59 mmol/L without physiologic consequences	N/A	> ULN − 10 mg/dL ≤ 0.59 mmol/L with physiologic consequences	> 10 mg/dL > 0.59 mmol/L life-threatening consequences

ALT = alanine aminotransferase (serum glutamic pyruvic transaminase), AST = aspartate aminotransferase (serum glutamic oxaloacetic transaminase), GGT =  $\gamma$ -glutamyl transpeptidase, LLN = lower limit of normal, N/A = not applicable, ULN = upper limit of normal, WBC = white blood cell.

Based on Common Terminology Criteria for Adverse events (CTCAE) Version 4.0. Published: May 28, 2009 (v4.03: June 14, 2010).

### 13.2 Classification of Chronic Kidney Disease

Stage	Description	GFR (mL/min/1.73m 2 )	Action*
	At increased risk	≥90 (with CKD risk factors)	Screening CKD risk reduction
1	Kidney damage with normal or GFR	≥90	Diagnosis and treatment: Treatment of comorbid conditions, slowing progression, CVD risk reduction
2	Kidney damage with mild GFR	60-89	Estimating progression
3	Moderate GFR	30-59	Evaluating and treating complication
4	Severe GFR	15-29	Preparation for kidney replacement therapy
5	Kidney Failure	<15 (or dialysis)	Replacement (if uremia present)

Shaded area identifies patients who have chronic kidney disease; unshaded area designates individuals who are at increased risk for developing chronic kidney disease. Chronic kidney disease is defined as either kidney damage or GFR <60 mL/min/1.73 m2 for 3 months. Kidney damage is defined as pathologic abnormalities or markers of damage, including abnormalities in blood or urine tests or imaging studies.

Abbreviations: GFR, glomerular filtration rate; CKD, chronic kidney disease; CVD, cardiovascular disease.

\* Includes actions from preceding stages.

